#### 17. BIOMARKER ANALYSIS

Frequency tabulations (number and percentages) for categorical variables and summary statistics for continuous variables will be provided in terms of actual value and changes from baseline for each visit.

Document:

Author:

Version Number:

V2.0

Version Date:

31JAN2024

Template No.: CS TP BS016 Revision 7 Reference: CS WI BS005

Effective Date: 01Nov2021

Statistical Analysis Plan

Page 62 of 78

For the below mentioned biomarkers- data will be analyzed:

#### 18. SAFETY OUTCOMES

In order to assess the long-term safety and tolerability of efgartigimod in participants, the below safety endpoints are considered within the secondary objectives.

- Incidence and severity of TEAEs
- Incidence and severity of AESIs
- Incidence and severity of SAEs
- changes in clinical laboratory safety results
- · vital signs, and
- electrocardiogram (ECG) results

These endpoints will be assessed and reported based on the SAF.

There will be no statistical comparisons between the treatment groups for safety data, unless otherwise specified with the relevant section.

#### **18.1.** Adverse Events

AEs and SAEs will be collected as defined in the Section 10.3 of the protocol. AEs will be coded using latest version of Medical Dictionary for Regulatory Activities (MedDRA) central coding dictionary. AEs will be graded using the National Cancer Institute (NCI) Common Terminology Criteria for Adverse Events (CTCAE) version 5.0. For each AE, start and stop date/times are collected as well as severity, a seriousness flag, treatment-relatedness, relatedness to procedures, action taken towards the study drug and outcome.

**Treatment-emergent adverse events (TEAEs)** are defined as AEs with onset on or after the first administration of IMP up to and including 60 days after the last IMP administration before the event (refer to schematic).

Document:

Author:

Version Number:

V2.0

Version Date:

31JAN2024

Template No.: CS TP BS016 Revision 7 Reference: CS WI BS005

Effective Date: 01Nov2021

Statistical Analysis Plan

Page 63 of 78

D1: IMP start	D40: Start IMP interruption		D120: IMP restart	D160: Start IMP disc		D240: Study disc
IMP			IMP			
TE: D1-D40	TE: D40+60 days	Non-TE: D101-119	TE:D120- D160	TE: D160+60 days	Non-TE: >D220	

AEs will be considered treatment-emergent based on their start date/time. If the AE start date/time is incomplete or missing, the AE will be considered treatment-emergent unless the available part of the AE start or stop date/time provide evidence that the event did not occur within 60 days from last IMP administration before the event.

AE onset and duration will be calculated as follows when start and stop dates are fully known:

- AE onset day (versus first administration)
  - $\circ$  AE start date ≥ date of first administration: AE start date date of first administration + 1 day.
  - o AE start date < date of first administration: AE start date date of first administration.
- AE duration (days) =
  - o AE end date AE start date + 1 day.
  - study discontinuation date AE start date + 1 day (when the AE start date is fully known but the AE is not resolved at the end of the study). In this case the duration will be presented as ">x days".

An AE for which the study drug was discontinued is defined as an AE with action taken "drug withdrawn".

**Severity** is classed as mild/ moderate/ severe/ life-threatening/ death. If a participant reports a TEAE more than once within that SOC/ PT, the AE with the worst-case severity will be used in the corresponding severity summaries.

**Relationship**, as indicated by the Investigator, is classed as "not related" or "related". If a participant reports the same AE more than once within that SOC/PT, the AE with the worst-case relationship to IMP will be used in the corresponding relationship summaries.

**AEs leading to discontinuation of IMP** will be identified by using the "Action taken with Efgartigimod/Placebo due to adverse event" from the AE page of the eCRF.

Adverse event of special interest (AESI) can be serious or nonserious, related, or unrelated to the IMP or study

Document:

Author:

Version Number: V2.0

Version Date: 31JAN2024

Template No.: CS TP BS016 Revision 7 Reference: CS WI BS005

Effective Date: 01Nov2021

Statistical Analysis Plan

Page 64 of 78

procedures. Infections are considered AESIs and are defined as events with a PT that falls under the MedDRA SOC 'Infections and infestations'.

**Infusion related reactions (IRRs)** are defined as all AEs with a MedDRA PT that is listed in either:

- MedDRA Hypersensitivity SMQ broad selection.
- MedDRA Anaphylactic reaction SMQ broad selection.
- MedDRA Extravasation events (injections, infusions and implants) SMQ broad selection, excluding implants. and occurs within 48 hours of an infusion/injection, or within 2 days if the AE start time is not available. In case of partially missing AE start date, the AE will be considered an IRR, unless the available parts of the AE start date provide evidence it did not occur within 48 hours of an infusion/injection.

Any deaths during the study are recorded on the "Deaths Details" page of the eCRF. A death case is defined as an AE with outcome 'fatal'. Fatal events will be presented in a summary table presenting overall TEAEs and a data listing along with primary cause of death.

Summary tables will only include TEAEs. However, all AEs reported during the study will be listed. Summary tables by SOC and PT will be sorted alphabetically.

An overview table of AEs will be presented by treatment to show number and percentage of participants with at least one event, the number of events, and the event rate per 100 PYFU for the following;

- TEAEs
- Serious TEAEs
- Grade ≥3 TEAEs
- Fatal TEAEs
- Treatment-related TEAEs according to the Principal Investigator
- Procedures-related TEAEs
- Serious treatment related TEAEs
- TEAEs leading to IMP discontinuation
- TEAEs leading to IMP interruption
- TEAEs of special interest
- IRRs

The overview table will also include a 95% Agresti- Min CI (in case of <30 participants in each group) or a 95% Newcombe CI (in case of ≥30 participants in each group) CI for the difference in AE rate between efgartigimod and placebo.

Document:

Author:

Version Number:

V2.0

Version Date:

31JAN2024

Template No.: CS TP BS016 Revision 7 Reference: CS WI BS005

Effective Date: 01Nov2021

Statistical Analysis Plan

Page 65 of 78

The event rate per 100 PYFU is defined as 100 \* the number of events divided by the sum of the follow-up time during which an event is considered treatment-emergent of all participants per treatment arm expressed in years (i.e. divided by 365.25).

All AEs, including pretreatment events will be listed.

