## 4. STUDY DESIGN

# 4.1. Overall Design

This is a randomized, double-blinded, placebo-controlled, phase 2, multicenter study.

For participants not enrolling in the OLE study, the study duration is approximately 36 weeks, spanning the following study periods:

• Screening:  $\leq 4$  weeks

• Treatment: 24 weeks

• Follow-up: 56 days

For participants enrolling in the OLE study, the study duration is approximately 28 weeks, spanning the following study periods:

• Screening:  $\leq 4$  weeks

• Treatment: 24 weeks

The study population includes adult participants with pSS, per ACR/EULAR 2016 classification criteria, with at least a moderate level of systemic disease activity (ESSDAI  $\geq$  5).

Participants will be randomized to receive efgartigimed IV 10 mg/kg or placebo in a 2:1 ratio, respectively.

All participants will receive efgartigimod IV 10 mg/kg or placebo once weekly for 24 weeks during the treatment period.

IMP will be administered as an approximately 1-hour IV infusion by site staff or a home nurse. The final dose will be administered at week 23.

At week 24, eligible participants may roll over to the single-arm OLE study.

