# 4.4. End-of-Study Definition

The end-of-study is defined as the date of the last participant's last visit.

A participant will have completed the study if the treatment period (or follow-up period, if applicable) has been completed.

• Participants rolling over to the OLE study will have completed this study at week 24

• Participants not rolling over to the OLE study will have completed this study after the SFV or EDV. If a participant continued in the study after discontinuing IMP, this will be week 24 or at the SFV (if permanent IMP discontinuation is < 56 days from week 24).

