# 6.7. Continued Access to IMP After the End of the Study

At the end of the study, argenx will comply with all local laws and regulations to ensure participants have continued access to IMP considered medically essential.

At week 24 (visit 25) eligible participants will have the option to enroll in the OLE study, where all participants will be treated with efgartigimod IV.

Participants will be ineligible for OLE study enrollment if either of the following criteria apply:

- Permanently discontinued from IMP (regardless of whether the participant completed the study)
- Discontinued from the study

Participants who complete the week 24 (visit 25) visit while temporarily interrupted from IMP (refer to Section 7.1.1) may enroll in the OLE study at the discretion of the investigator. These participants will enter the OLE study but will not be dosed with efgartigimod IV until they meet the relevant conditions specified by the protocol for the OLE study.

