## 8.4.1. Time Period and Frequency for Collecting AE and SAE Information

All AEs will be collected from the signing of the ICF until the SFV, as specified in the SoA (Section 1.3).

All SAEs and AESIs will be recorded and reported to the sponsor or designee immediately, and under no circumstance will this exceed 24 hours, as indicated in Appendix 3 (Section 10.3). The investigator will submit any updated SAE data to the sponsor within 24 hours of being available.

Investigators are not obligated to actively seek information on AEs or SAEs after the conclusion of the study participation. However, if the investigator learns of any SAE, including death, at any time after a participant has been discharged from the study, and they consider the event to be reasonably related to IMP or study participation, the investigator must promptly notify the sponsor.

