#### 3. STUDY DESIGN

## 3.1. General Description

This study aims to evaluate the efficacy and safety of infusions of efgartigimod, a human neonatal crystallizable fragment receptor (FcRn) antagonist that can rapidly reduce IgG, including pathogenic antibodies. Efgartigimod has the potential to successfully treat pSS and improve disease manifestations by the reduction of IgG autoantibodies in pSS.

This is a randomized, double-blinded, placebo-controlled, phase 2, multicenter study, with an open-label extension (OLE) study.

For participants not enrolling in the OLE study, the study duration is approximately 36 weeks,

spanning the following study periods:

- Screening:  $\leq 4$  weeks
- Treatment: 24 weeks
- Follow-up: 56 days (after final dose)

For participants enrolling in the OLE study, the study duration is approximately 28 weeks, spanning the following study periods:

Document:

Author:

Version Number:

V2.0

Version Date:

31JAN2024

Template No.: CS TP BS016 Revision 7 Reference: CS WI BS005

Effective Date: 01Nov2021

Statistical Analysis Plan

Page 19 of 78

Screening: ≤ 4 weeksTreatment: 24 weeks

The study population includes adult participants with pSS, per ACR/EULAR 2016 classification criteria, with at least a moderate level of systemic disease activity (ESSDAI  $\geq$  5). Participants will be randomized using interactive response technology (IRT) to receive efgartigimod IV 10 mg/kg or placebo in a 2:1 ratio, respectively.

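### The between-arm adverse-event percentages and their confidence interval pool completers seen to week 24 with completers seen about seven weeks longer, so they can be biased if rollover to the extension differs by arm

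*SAP*

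**What the plan says.** Protocol section 4.1 sets the end of dosing: "The final dose will be administered at week 23". Section 4.4 then separates two groups. For the first, "Participants rolling over to the OLE study will have completed this study at week 24". The others who finish dosing go on to the safety follow-up visit (SFV). SAP section 3.1 lists this period as "Follow-up: 56 days (after final dose"), and Protocol section 7.1.1 gives the visit a window of ±3 days. Protocol section 8.4.1 ties event collection to that visit: "All AEs will be collected from the signing of the ICF until the SFV".

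SAP section 18.1 defines one treatment-emergent window for all participants, from the first dose "up to and including 60 days after the last IMP administration before the event". It has no separate rule for participants who roll over. Event percentages use every participant in the arm as denominator (SAP section 7.2). The overview table adds an Agresti-Min or Newcombe interval for the "difference in AE rate between efgartigimod" and placebo. It also gives event rates per 100 person-years of follow-up (PYFU), with the denominator defined as "the sum of the follow-up time during which an event is considered treatment-emergent of all participants per treatment arm". The tables by system organ class and preferred term in section 18.1.1 give counts and percentages only.

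Protocol section 6.7 bars from the extension anyone who has "Permanently discontinued from IMP (regardless of whether the participant completed the study") or left the study.

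**The concern.** Rollover happens after randomisation. It is optional, and it excludes people who stopped treatment, so it may depend on response and tolerability, and so on treatment arm. A completer who stays out of the extension has about seven more weeks in which an event can be counted. A crude percentage takes no account of that, and neither do the two named interval methods, which are for differences between proportions. SAP section 18 rules out statistical comparison of safety data unless a section specifies one, and this interval is the one that section 18.1 specifies.

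Safety compared with placebo is a secondary objective, and infection is the adverse event of special interest. If more efgartigimod completers roll over, the placebo arm is watched longer, and an excess of infections on efgartigimod could look smaller than it is.

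**Working it through.** **Day counts.** The first dose is study day 1 (SAP section 6.1).

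- Last dose, week 23: 23 × 7 + 1 = day 162.
- Week 24: 24 × 7 + 1 = day 169, the target day in SAP Tables C and D.
- SFV: 162 + 56 = day 218 (215 to 221 with ±3 days).
- End of treatment-emergent window: 162 + 60 = day 222.

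The window rule reproduces the schematic in SAP section 18.1: day 40 + 60 = day 100, so non-emergent time starts on day 101; day 160 + 60 = day 220. The gap 218 − 169 = 49 days also agrees with the follow-up of about 7 weeks noted in SAP section 6.3.

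**Observation among those who finish dosing.** Rollovers are seen for 169 − 162 = 7 of the 60 days after the last dose, non-rollovers for 56 of 60. Total observation is 169 versus 218 days; 218/169 = 1.29.

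**Bias in the crude percentage with no true effect.** All of the following are assumptions: one constant hazard in both arms, during and after dosing; a 50% risk of at least one event by day 169; every non-rollover completed dosing and was seen to day 218.

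- Hazard: ln 2 / 169 = 0.00410 per day.
- Risk by day 218: 1 − exp(−0.00410 × 218) = 0.591.
- Arm percentage with rollover share r: r × 0.500 + (1 − r) × 0.591.

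| Assumed rollover, efgartigimod / placebo | Efgartigimod | Placebo | Spurious difference (efgartigimod − placebo) |
|---|---|---|---|
| 90% / 90% | 50.9% | 50.9% | 0 |
| 90% / 80% | 50.9% | 51.8% | −0.9 points |
| 90% / 60% | 50.9% | 53.6% | −2.7 points |
| 100% / 0% | 50.0% | 59.1% | −9.1 points |

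**What early stopping does to this.** A participant who stops treatment cannot roll over, and the window then closes 60 days after the earlier last dose. It closes before day 169 whenever the last dose falls before day 169 − 60 = day 109. For a last dose at week 10 (day 71) it closes on day 131, and the same hazard gives a risk of 1 − exp(−0.00410 × 131) = 0.416. If every non-rollover were such a person, the 90% / 60% case gives 0.9 × 0.500 + 0.1 × 0.416 = 49.2% against 0.6 × 0.500 + 0.4 × 0.416 = 46.6%, a difference of +2.5 points before rounding. The sign reverses.

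**Comparison with sampling error.** With about 20 and 10 participants and a 50% risk, the standard error of the difference is √(0.25/20 + 0.25/10) = 0.194, and the Wald 95% half-width is 1.96 × 0.194 = 0.38, or 38 points.

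**The case against.** The strongest reply is that the plan already handles much of this. The overview reports rates per 100 PYFU for all, serious and special-interest events, so infections have an exposure-adjusted summary. SAP section 8.1 tabulates rollover. Safety is descriptive, the study tests no formal hypothesis, and a bias of 1 to 3 points is small beside a half-width of about 38. All of that stands, and it limits the weight of the point. It does not help the percentages or their interval, which carry no adjustment, nor the tables by organ class.

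Three stronger readings are tempting, and the documents do not support them.

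- A reader might infer that the arms are in fact compared over unequal follow-up. That requires rollover, or the timing of stopping, to differ by arm, and the documents give no expected shares.
- A reader might infer that the PYFU denominator credits each rollover to day 222, adding 222 − 169 = 53 unobserved days and understating that person's rate by 1 − 169/222 = 24%. The definition speaks of "the sum of the follow-up time during which an event is considered treatment-emergent of all participants per treatment arm". A rollover's follow-up in this study ends at week 24, so the natural reading stops there. What remains is that the SAP does not state the stopping point.
- A reader might infer that events on efgartigimod in the extension are counted against placebo. The extension is a separate study (ARGX-113-2211), and the protocol's schedule of activities monitors events only to the last study-related activity. Nothing says that extension events enter these tables.

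**Conclusion.** The point holds in a limited form. Observation after the last dose differs by design between completers who roll over and those who do not, and the one specified between-arm comparison of adverse events ignores this. The possible bias is zero with equal rollover and equal stopping patterns. Under the stated assumptions it is about 1 point at 90% versus 80% rollover, 2.7 at 90% versus 60%, and 9 at the extreme of 100% versus 0%. Rollover shares, the 50% risk and the constant hazard are all assumed.

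The direction is not known either. It would be wrong to conclude that the arm with fewer rollovers is always watched longer: that is so when its non-rollovers completed dosing, and it can reverse when they stopped early. The person-time rates address the problem only in part. This is a cheap improvement to the SAP, not an error that undermines the study.

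**What to change.** In SAP section 18.1:

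- Base the between-arm overview percentages and their confidence interval, and the key special-interest and serious event tables, on events with onset up to the week 24 visit and before any extension dose. Cut the PYFU denominator at the same point.
- Keep the full treatment-emergent summary (last dose + 60 days) beside it. End both events and PYFU at the earliest of last dose + 60 days, last visit in this study, and first extension dose.
- Show follow-up time by arm next to the rollover counts already planned.

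Numerator and denominator must share one cut-off. Counting events to week 24 while running person-time to the SFV would understate the rate of a completer who does not roll over by 1 − 169/218 = 22%.

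The cost is SAP wording and one extra set of tables; no new data are needed. Post-treatment events fall outside the between-arm interval but are still reported. A common week 24 cut removes the difference due to rollover among completers. It does not equalise the shorter windows of participants who stop treatment early, which is why follow-up time by arm should be shown.

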#### **18.1.1. All TEAEs**

Summary tables will only include TEAEs and will be presented by System Organ Class (SOC) and Preferred Term (PT) for each treatment group. Table will contain number and percentage of participants with at least one event and the number of events (except for TEAEs by worst toxicity) for TEAE. These outputs will be provided for:

- TEAEs
- Serious TEAEs
- Nonserious TEAEs
- Grade ≥3 TEAEs
- TEAEs by worst toxicity
- Treatment-related TEAEs
- Procedure-related TEAEs
- Serious treatment-related TEAEs
- TEAEs leading to IMP discontinuation
- TEAEs of special interest
- IRRs
- Serious IRRs

#### 18.2. Laboratory Evaluations

Results from the central laboratory will be included in the reporting of this study for serum chemistry and hematology, coagulation, urinalysis, serology (e.g. viral marker testing), and specialty laboratory parameters. A list of laboratory assessments to be included in the outputs is included in Appendix 2 (Table 6) of the protocol.

These are mainly as follows.

Document:

Author:

Version Number:

V2.0

Version Date:

31JAN2024

Template No.: CS TP BS016 Revision 7 Reference: CS WI BS005

Effective Date: 01Nov2021

Statistical Analysis Plan

Page 66 of 78

#### **Laboratory Assessments**

Hematology	RBC count, platelet count, hemoglobin, hematocrit, MCV, MCH, WBC count with differential: neutrophils, eosinophils, lymphocytes, basophils, monocytes
Serum chemistry	ALT, AST, albumin, blood urea nitrogen, creatinine, eGFR, glucose, potassium, chloride, bicarbonate, sodium, total protein, calcium, bilirubin (total and direct) creatine kinase, HbA1C, HDL, LDL, triglycerides, C-reactive protein
Routine urinalysis	Specific gravity, pH, glucose, protein, blood, ketones, bilirubin, urobilinogen, nitrite, leukocyte esterase, microscopic examination (if blood or protein is abnormal)  Urine protein quantitative analysis (if protein is abnormal)
Pregnancy testing	Highly sensitive serum hCG pregnancy serum test at screening and urine test at other time points (as needed for WOCBP potential,)
Other tests	SARS-CoV-2 nasopharyngeal swab test (PCR) (if applicable)  HBV, HCV, HIV  Menopausal test (FSH) if applicable (to confirm non-WOCBP status)  IgG a

a This result will be blinded postbaseline.

 $ALT= a lanine\ aminotransferase;\ AST= a spartate\ aminotransferase;\ BUN= blood\ urea\ nitrogen;\ FSH= follicle-stimulating\ hormone;$ 

Document:

Author:

Version Number:

V2.0

Version Date:

31JAN2024

Template No.: CS\_TP\_BS016 Revision 7 Reference: CS\_WI\_BS005

Effective Date: 01Nov2021

Statistical Analysis Plan

Page 67 of 78

GFR=glomerular filtration rate; HbA1C=glycated hemoglobin; HBV=hepatitis B virus; hCG=human chorionic gonadotropin; HCV=hepatitis C virus; HDL=high-density lipoprotein; IgG=immunoglobulin G; LDL=low-density lipoprotein; MCH=mean corpuscular hemoglobin; MCV=mean corpuscular volume; PCR=polymerase chain reaction; RBC=red blood cell; WBC=white blood cell; WOCBP=women of childbearing potential

Normal ranges are available as provided by the central laboratory and results will be presented in standardized units unless specified otherwise. Clinically significant changes occurring during the study are recorded as an AE.

Quantitative laboratory measurements reported as "< X", i.e. BLQ, or "> X", i.e. above the upper limit of quantification (ULQ), will be converted to X for the purpose of quantitative summaries, but will be presented as recorded, i.e. as "< X" or "> X" in the listings.

Continuous laboratory parameters will be summarized using descriptive statistics of actual values and changes from baseline at each analysis visit. Categorical parameters will only be listed.

The following summaries will be provided for laboratory data:

- Continuous laboratory parameters to be summarized using descriptive statistics of actual values and changes from baseline at each analysis visit.
- Laboratory toxicity grades to be presented as cross-tabulations of the toxicity at each postbaseline analysis visit
  and at the worst-case analysis visit versus the baseline toxicity.
- Laboratory abnormalities as cross-tabulations of the abnormality at each postbaseline analysis visit and at the
  worst-case analysis visit versus the baseline abnormality. The number of participants with treatment-emergent
  abnormalities will also be shown. The denominator for the percentage is the total number of participants per
  treatment arm and per analysis visit in the SAF.
- Listing of participants with any post-baseline abnormality or toxicity grade ≥1.

